2.2 Setting/Location

Research will be conducted through the MyChart electronic medical records system with patients of Inova Health Systems primary care offices (27 locations). Half of the 27 primary care offices will be randomly selected to receive treatment, but outcome data (existing electronic medical records data) will be analyzed for the entire study population.

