3.3 Randomization

Provider-side treatments will be cluster randomized at the practice level. Randomization will stratify across practices by number of diabetic patients (cluster size), and will be conducted using a random number generator at the outset of the study. Reminder messaging treatments will be assigned alphabetically by first two letters of patient last name, as it is logistically infeasible to do individual level patient messaging without sorting on an existing field in the patient's EHR. There are some concerns that ethnicity could correlate with assignment based on last name spelling, so this form of assignment is "pseudo-random". However, the patient's race/ethnicity recorded in the medical record will be controlled for in the analysis. Causal interpretation of the results of the reminder messaging portion of the experiment will thus require the assumption that grouped last name spelling is not independently related to likelihood of flowsheet adoption.

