4.1 Sample Size

Non-pregnant adult patients of Inova primary care physicians with a current diabetes mellitus diagnosis and active MyChart account at time of treatment administration will be included in the study. The estimated number of patients is around 7200, from 71 primary care physicians across 24 selected Inova primary care practices.

Power Calculations

Power calculations were performed using the “clustersampsi” command in Stata. Knowledge of available sample and estimates/assumptions of control outcome mean, variance, and intraclass correlation were used to calculate a minimum detectable effect size for the key outcomes of flowsheet adoption (extensive margin, dichotomous rate of adoption) and changes in mean A1c.

Flowsheet Adoption: Practice Level Treatment-Control Comparison

Sample Size: 7200

Number of Treatment Arms: 2

Number of Clusters: 24

Assumed Control Adoption Rate: 2%

Assumed Intra-Cluster Correlation (within practices): 0.1

Minimum Detectable Effect: **9.5 percentage point increase in flowsheet orders**

Mean HbA1c: Practice Level Treatment Control Comparison

Sample Size: 7200

Number of Treatment Arms: 2

Number of Clusters: 24

Assumed Control HbA1c Mean: 6.74

Assumed Control HbA1c Standard Deviation: 1.39

Assumed Intra-Cluster Correlation (within practices): 0.07

Assumed Baseline Correlation: 0.80

ITT Minimum Detectable Effect: **0.27 change in A1c**

Flowsheet Adoption: Individual Level Comparison between Messaging Assignment Groups in Treatment Practices

Sample Size: 3600

Number of Arms (including no reminder): 4

Assumed No Reminder Adoption Rate: 20%

Minimum Detectable Effect: **5.5 percentage point increase in use of flowsheets when compared to no reminder**

Justification

The sample size represents the entire population of Inova primary care patients with diabetes who have active MyChart accounts and are therefore able to access the blood glucose tracking feature. The minimum detectable effects resulting from power calculations above are in-line with similar studies cited in the protocol background. Metastudy reviews of the effect of self monitoring of blood glucose found a 0.33 point change in A1c.

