4.2 Method of Data Analysis

All data analyzed in this study will be administrative health and use data that is collected as part of routine medical care and record keeping. EPIC has offered to build the SQL queries required to produce the outcome datasets described in this protocol. Outcomes listed in Section 3.4. will be analyzed using regression analysis, including (a) a version with no covariates, (b) a version controlling for patient age/gender, race/ethnicity, A1c at baseline, days since most recent office visit at baseline, and doctor fixed effects. A flag identifying patients who are eventual participants of "Impact of Innovative Interventions on Diabetic Adherence with Digital Sensors" (a study recently submitted to the IRB that may have limited overlap with this population) will also be included in the controls. For outcomes indicating analysis of practice level treatment and control groups, standard errors will be clustered at the practice level.

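### With 24 practices of unequal size and no small-sample method named, the nominal 5% practice-level test of mean A1c can run at about 6 to 8.5%

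*Combined protocol and SAP*

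**What the plan says.** Section 4.2 sets out the analysis: "Outcomes listed in Section 3.4. will be analyzed using regression analysis, including (a) a version with no covariates", and a version (b) that adds patient covariates, baseline A1c and doctor fixed effects. For comparisons of treatment and control practices it adds only that "standard errors will be clustered at the practice level". It does not name the cluster-robust variant, the reference distribution or the degrees of freedom, and it mentions no bootstrap or randomisation test.

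Section 4.1 describes the sample: "The estimated number of patients is around 7200", "from 71 primary care physicians across 24 selected Inova primary care practices". Section 2.2 counts 27 offices ("Half of the 27 primary care offices will be randomly selected to receive treatment"), which fits 24 once the three sites excluded in Section 2.5 are removed. Section 3.3 shows that the authors expect practices to differ in size: "Randomization will stratify across practices by number of diabetic patients (cluster size"). No size distribution is given.

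**The concern.** The usual cluster-robust (sandwich) variance is biased downwards when clusters are few. When clusters also differ in size, a few large ones dominate the estimate, and the effective degrees of freedom fall well below the number of clusters minus one. Referring the statistic to t on 23 degrees of freedom, or to the normal, then gives intervals that are too narrow and too many false positives.

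Mean A1c is where this matters, because Section 3.4 tests it between treatment and control practices and the health conclusion rests on it. Leaving the variant unnamed also means that the choice could be made after the results are seen.

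**Working it through.** **Inputs from Section 4.1.** 7200 patients and 24 practices, so 300 per practice on average and 12 per arm. A1c: "Assumed Control HbA1c Standard Deviation: 1.39"; "Assumed Intra-Cluster Correlation (within practices): 0.07"; baseline correlation 0.80. Control adoption 2%, with an intra-cluster correlation (ICC) of 0.1.

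**Assumptions.** 5% two-sided and 80% power (not stated, but they reproduce the plan's figures). Practice-size CV of 0 to 0.8 (not given).

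**Step 1: the plan's own figure.**
- Design effect with equal sizes: 1 + 299 × 0.07 = 21.93.
- SE of the difference: 1.39 × √((1 − 0.8²) × 21.93 × 2/3600) = 0.0921.
- With t quantiles on 22 df: (2.074 + 0.858) × 0.0921 = 0.270.
- With normal quantiles: 2.802 × 0.0921 = 0.258.

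The plan states 0.27. The adoption figure behaves in the same way: 9.45 to 9.63 points with t(22) and 8.9 to 9.0 with normal quantiles, against a stated 9.5. The power calculation therefore allowed for few clusters.

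**Step 2: equal sizes, worked exactly.** With 12 practices per arm, the uncorrected sandwich variance averages 11/12 of the true value. The usual CR1 factor is (24/23) × (7199/7198). The product is 0.957, so the SE is 0.978 of what it should be.
- Critical value from t(23): 2.069 × 0.978 = 2.023, which on 22 df gives a type I error of 5.5%.
- Normal critical value: 1.960 × 0.978 = 1.917, which gives 6.8%.

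**Step 3: unequal sizes, by simulation under no effect.** Patient-level difference in mean A1c without covariates, ICC 0.07, 24 practices, allocation stratified by size, CR1 with t(23), 20,000 runs per cell:

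| Size CV (assumed) | Type I error |
|---|---|
| 0 | 5.6% |
| 0.4 | 6.4% |
| 0.6 | 7.1% |
| 0.8 | 8.4% |

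Over the same CV range, normal critical values give about 7 to 10%. At CV 0.6, an ICC of 0.02 or 0.10 gives 7.0 to 7.7%, and 27 practices with 9000 patients give about 7.5%. Section 6.2 mentions 10 selected practices; a 10 versus 14 split gives 5.7 to 8.4%.

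**Step 4: adoption and entry counts.** Under the null the control condition applies: 2% adoption, ICC 0.1. Entries per adopter were assumed skewed (mean 30, gamma shape 0.7). The same test of counts then runs at 3.2 to 4.4%, and the binary adoption test at about 3 to 5%.

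**Step 5: the alternatives.** A randomisation test that respects the size strata gives about 4.6 to 5.5% for A1c and 4.3 to 5.4% for counts. CR2 errors with Satterthwaite df give 4.3 to 5.0% for A1c (CV 0 to 0.8) when the working model includes the ICC. The effective df are then 22, 14, 10 and 7 at CV 0, 0.4, 0.6 and 0.8. For counts CR2 is conservative (1.3 to 4.8%).

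**The case against.** The strongest reply is that the text is silent, not wrong. It excludes no correction, and the power calculation used t quantiles, so the authors may intend a suitable method. That is fair as far as it goes: the documents do not show that a correction was rejected. But the stated rule, carried out in the usual way, is anti-conservative for A1c, and allowing for few clusters in planning does not bind the analysis.

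The size of the problem also rests on a CV that the documents do not give. This stands. With equal sizes the excess is about half a point, so 24 practices alone are not the main driver; unequal size is.

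Section 1.1 examines health effects only if adoption rises significantly. That limits false A1c claims when the intervention does nothing. It gives no protection if adoption rises and A1c does not move.

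A reader might infer that entry counts are inflated too. The plan's own inputs do not support this (step 4). Inflation appears only with a much lower ICC (0.01 to 0.02 gives 4.7 to 6.8%) or higher null adoption (20% gives 5.0 to 8.1%). No ICC is given for counts, and the 20% in Section 4.1 is the assumed no-reminder rate inside treatment practices, not the control rate.

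Finally, only version (a) was simulated. The rates are not shown to carry over to version (b), where doctor fixed effects would absorb a practice-level treatment if doctors are nested in practices. That is a separate problem.

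**Conclusion.** The point holds for mean A1c, for the analysis without covariates, and on the assumption that CR1 errors with t(23) are what the plan means. The excess over 5% is about half a point with equal sizes and about 1 to 3.5 points at the assumed CVs of 0.4 to 0.8. It is larger with normal critical values. It changes little with the ICC or with 24 versus 27 practices.

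It does not extend to inflated adoption or entry-count tests. Those err slightly in the conservative direction at the plan's inputs, which is a further reason to use a method that holds its level for all of these outcomes. The change should be made before outcome data are analysed.

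**What to change.** In Section 4.2, for every practice-level contrast:

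- Take the primary p-value from a randomisation test that re-draws the practice allocation within the size strata actually used. State that this p-value decides significance, so that a disagreement with an interval has a rule. The test is exact under no effect, including for rare or skewed outcomes. Record the strata and the allocation procedure so that the re-draws match them.
- For A1c, report confidence intervals from CR2 standard errors with Satterthwaite degrees of freedom, and state the working model. The choice matters: under an independence working model the df are about 14 to 22, while including the ICC takes them down to about 7 at CV 0.8.
- For skewed counts, obtain intervals by inverting the randomisation test, because CR2 intervals can be too wide.
- Keep plain clustered errors as a sensitivity analysis.

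**Cost.** Plan wording and a few lines of code, with no change to data or design. A1c intervals become modestly wider. At CV 0.6 the design effect is 1 + (1.36 × 300 − 1) × 0.07 = 29.49, so the minimum detectable effect rises from 0.270 to 0.313 through unequal sizes alone, whatever the method. Moving from 22 to about 10 df takes it to 0.332, a further 6%.

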4.3 Data Storage

All data will be stored on Inova systems, and authorized collaborating researchers and personnel will access the data remotely through Citrix. A data use agreement (draft attached) will be entered into by Inova and the General Services Administration, and specified personnel from GSA will be authorized to

access the limited dataset and perform data analysis. The limited dataset accessed through Citrix will be have facial identifiers removed in accordance with the HIPAA definition of limited dataset and personnel authorized to access will agree to (i) not use or disclose the information other than as permitted by the DUA or as otherwise required by law; (ii) use appropriate safeguards to prevent the use or disclosure of the information other than as provided for in the DUA; (iii) report to Inova any use or disclosure of the information not provided for by the DUA of which the recipient becomes aware; and (iv) not to identify the information or contact the individual. Data will be fully anonymized and linkages to identifying information will be permanently destroyed three (3) years after the conclusion of the study.

5. Human Subjects Protections

5.1 Risks

The risks to participation in this study are minimal. The randomized encouragement design means that doctors will make the final determination of whether use of electronic blood glucose flow sheets is suitable for the patient. The study does not advise against or preclude the provider or patient from switching to alternative methods for self monitoring of blood glucose, or using other forms of treatment concurrently. Previous research has shown positive health effects of self monitoring of blood glucose, and it is a recommended treatment for diabetes. However, one low risk area is potential loss of privacy. The risk will be minimized by implementing an adequate plan to protect the identifiers from improper use and disclosure: a limited dataset will be created and made available to authorized researchers via remote access on Citrix. Data will be fully anonymized and linkages to identifying information will be permanently destroyed three (3) years after the conclusion of the study. Protected health information will not be reused or disclosed to any other person or entity, except as required by law, or for authorized oversight of the research project.

5.2 Benefits

The intervention seeks to test methods for increasing utilization of an existing feature of the MyChart EHR system. Lessons from this aspect of the study may be applied to increase awareness and utilization of other new EHR features, potentially benefiting patients and doctors indirectly.

Patients who decide to track their blood sugar through MyChart as a results of the intervention may experience increased ability to control and manage their diabetes. Because providers will be able to view and interpret blood glucose data more easily and frequently, they may be more likely to adjust and tailor treatment plans to this information. Both of these factors may lead to improved patient health indicators (specifically A1c).

5.3 Alternatives

Not applicable.

5.4 Confidentiality

To minimize the risk of loss of confidentiality, the research team will implement a plan to protect the identifiers from improper use and disclosure: a limited dataset will be created and made available only to authorized researchers via secure remote access to Inova systems on Citrix. Data will be fully anonymized and linkages to identifying information will be permanently destroyed three (3) years after the conclusion of the study. Protected health information will not be reused or disclosed to any other person or entity, except as required by law, or for authorized oversight of the research project.

6. Subject Compensation

6.1 Costs

There are no direct costs to participants. Indirect costs to patients may include inconvenience of receiving additional secure messages. Due to encouragement of flowsheet orders by physicians in the treatment group, patients choosing not to follow their doctor's recommendation of electronic glucose tracking may feel guilt, and patients choosing to complete the online flowsheets will need to spend additional time entering their values. Amount of time spent will depend on whether they set up an automatic download of electronic readings through their smartphone, or manually enter the values via an internet-connected device. If patients choose to start tracking their blood glucose and have not already been doing so, they may face additional supply costs.

6.2 Payment

There will be no payment for participation. A subset of participants in the treatment group--one quarter of patients with diabetes in 10 randomly selected practices--will have the chance to receive one of 50 \$50 gift card to Amazon.com if they choose to enter data into the flowsheet for any day during the study period (chance will be increasing in the number of days flowsheet is used). This gift card is intended as compensation to offset hassle costs of entering data into the flowsheet, and not as an incentive to participate in the study. Study personnel will follow guidelines from section 11.10 of IRC on the distribution of gift cards.

The code for online redemption of the gift card will be sent to selected recipients who remain MyChart activated at the time of distribution in a secure message through MyChart. The subject line will read Gift Card Recipient: MyChart Glucose Tracking Program. Patient replies will be disabled for this communication. We will track read-receipts after one month, but will not re-send messages or take any action based on this information. The message will read as follows:

We're pleased to let you know that you were selected to receive a \$50 gift card to Amazon.com! You were chosen for a special program through Inova to help you get started tracking your blood glucose through MyChart. For each day that you tracked your blood glucose on MyChart between May and August 2018, you were entered to receive one of fifty gift cards. You tracked, and one of your entries was randomly selected! To redeem your gift card, visit <https://www.amazon.com/gc/redeem> and enter [code].

7. Adverse Event Reporting

Risks from participation in this study are minimal, but one possible adverse event is breach of confidentiality. Adverse events will be reported in accordance with IRC 11.16.

8. Funding

Key Personnel [name] has received a small J-PAL North America HCDI Project Development grant (less than \$5000) to cover gift cards, and personal travel costs. The grant will be administered directly to [name] and will not pass through the Inova grant office.

9. Conflicts of Interest

None.

10. Facilities and Equipment

Data analysis will be conducted through remote access to Inova Citrix systems. The intervention will be administered primarily through MyChart, and will not require any additional equipment or facilities.

11. Outside Collaborators

